3.1.2 Responder Analyses of CGI-I and OSU CGI-I Improvement at [REDACTED] and [REDACTED]

For each of the endpoints CGI-I and OSU CGI-I, a table will be produced to present the number and percentage of subjects showing improvement at [REDACTED] (as compared to CGI-S (OSU CGI-S) (clinical presentation) at [REDACTED]), as well as the number and percentage of subjects showing improvement at [REDACTED] (as compared to CGI-S (OSU CGI-S) (clinical presentation) at [REDACTED]). 'Improvement' will be defined as a CGI-I (OSU

CGI-I) score <=3 at the respective time point (corresponding to scores of: 1 = Very much improved; 2 = Much improved; 3 = Minimally improved).

Each table will also present the p-value, obtained from McNemar's exact test, for the comparison between [redacted] and [redacted] of the proportion of subjects with improvement. This represents a comparison of improvement during active treatment compared to improvement during the [redacted] phase.

3.1.3 Bar Charts of Mean and SD by Visit for Selected Efficacy Endpoints

Bar charts will be produced for selected endpoints to present group mean +/-SD at [redacted] and [redacted] (except in the case of DXA Scan, CGI-I and OSU CGI-I results which will only be presented at [redacted] and [redacted]). At each visit, the mean value across all patients will be presented as a bar and the SD of the values at that visit will be presented as line extending above and below the top of each bar joining horizontal lines, denoting the mean +/- the SD. Subtitles, footnotes and axis labels will be adapted from the equivalent by subject line plots planned in this SAP for the respective endpoints, with an additional footnote to describe the presentation of mean values and SDs. The endpoints to be presented will be:

- Handgrip Myometry over Time (relaxation time, repeated for the dominant hand and non-dominant hand)
- Pulmonary Function Test (FVC) over Time
- Time Taken (Seconds) to Complete the Nine Hole Peg Test over Time (repeated for the dominant arm and non-dominant arm)
- Clinical Global Impression over Time (Improvement scores for [redacted] and [redacted])
- OSU Global Improvement Scale for Autism over Time (Improvement scores for [redacted] and [redacted])
- Peabody Picture Vocabulary Test over Time (age based standard score)
- DXA Scan (Body Composition - Lean Muscle Mass) over Time (arms category for [redacted] and [redacted])

3.1.4 Bar Charts of Percentage of Responders for CGI-I and OSU CGI-I at [redacted] and [redacted]

Bar charts will be presented for the percentage of subjects recording improvement at [redacted] and [redacted] for the CGI-I and OSU CGI-I endpoints. 'Improvement' will be defined as a score <=3 at the respective time point (corresponding to scores of: 1 = Very much improved; 2 = Much improved; 3 = Minimally improved). A subheading will present the dose group with the corresponding population total and any other subtitles per the equivalent by subject line plot planned in this SAP. The percentage of subjects will be calculated as the number of subjects recording a score <=3 at the respective time point as a percentage of the full analysis set.

3.1.5 Line Plots of Percentage Changes Over Time for Selected Efficacy Endpoints

Line plots will be presented to display the percentage change over time for total clinician-completed domain specific causes for concern VAS, and caregiver top 3 concerns total VAS.

Two plots will be presented for each endpoint, one to present the percentage change from [] to [], another to present the percentage change from [] to [] and []. On each plot, the percentage change will be presented by subject as well as the group mean percentage change +/- SD across all subjects.

3.1.6 Scatterplots of Visit [] Data for Selected Efficacy Endpoints

Scatterplots will be presented indicating observed values at [] for each subject on selected endpoints. Subject number will be presented on the x-axis with the respective [] observed value on the y-axis. Subtitles, labels and footnotes will be adapted from the respective by subject line plots planned in this SAP. Where the endpoint is presented for different categories (e.g. preferred/fastest speed or dominant/non-dominant hand), each category will be displayed on a separate page. The endpoints to be presented will be:

- Time to complete 10m walk test (repeated for preferred and fastest speed)
- Handgrip Myometry (Grip strength and Relaxation time, repeated for the dominant hand and non-dominant hand)
- Pulmonary Function Test (FVC)
- Nine Hole Peg Test (dominant arm)
- Clinician-completed domain specific causes for concern VAS (repeated for total and domain specific VAS scores)
- Caregiver Top 3 Concerns Total VAS
- Peabody Picture Vocabulary Test (age based standard score)

4 STUDY SUBJECTS

4.1 Disposition of Subjects

The number and percentage of all subjects enrolled, included in the full analysis set, safety analysis set, pharmacokinetic analysis set, who completed the study, prematurely discontinued treatment (where the subject discontinued prior to []), prematurely discontinued the study and study duration (date of completion/discontinuation – Visit [] date + 1) will be summarised. The number and percentage of subjects will be summarised by their reasons for withdrawal from treatment (i.e. prior to [] and separately from the study (i.e. prior to [])). Eligibility for each of the analysis sets along with reasons for exclusion will be listed. Study completion/withdrawal data will be listed.

4.1.1 Analysis Sets

The **Enrolled Set** includes all subjects who passed screening irrespective of whether they received active treatment. The enrolled set will be used for subject disposition summaries.

The **Safety Analysis Set (SAF)** will include all subjects who had at least one administration of active treatment. The SAF will be used for all summaries of protocol

deviations, background and demographic characteristics, administration of investigational product and safety evaluation data.

The **Full Analysis Set** (FAS) will include all subjects in the SAF for whom any efficacy data were collected after first administration of active treatment. The FAS is the primary population for analyses of efficacy data.

The **Pharmacokinetic Analysis Set** (PKAS) will consist of all subjects for whom PK plasma concentration data (which includes concentrations below the lower limit of quantification (LLOQ)) are available at either [REDACTED] or [REDACTED] (pre-dose or post-dose).

Listings of study data will be based on all subjects who were enrolled in the study.

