1 INTRODUCTION

This document details the statistical analysis of the data that will be performed for the AMO Pharma Ltd study: A Single-Blind, Phase 2 Study to Evaluate the Safety and Efficacy of Tideglusib 400mg or 1000mg for the Treatment of Adolescent and Adult Congenital and Juvenile-Onset Myotonic Dystrophy.

The proposed analysis is based on the contents of protocol version 4.0 (dated 09-JAN-2017). In the event of future amendments to the protocol, this statistical analysis plan (SAP) may be modified to account for changes relevant to the statistical analysis.

The table, listing and figure shells are supplied in a separate document.

The analysis and statistics reporting will be conducted at [REDACTED] using SAS version 9.2 or higher.

Summary statistics will consist of number of subjects(n), mean, standard deviation (SD), minimum, median and maximum, unless specified otherwise. The precision of these variables is defined in the table, figure and listing shells document.

For categorical variables, the number and percentage of subjects in each category will be presented, based on the number of non-missing observations apart from disposition of subjects, protocol deviations, background and demographic characteristics, prior and concomitant medications and adverse events where the percentage will be based on the number of subjects in the analysis set.

Where mentioned in this SAP, "active treatment" will relate to tideglusib treatment.

Unless otherwise stated, baseline is defined as the last non-missing value (including scheduled and unscheduled assessments) prior to the subject receiving active treatment.

In the final analysis of the combined Cohort 1 and Cohort 2 subject data, data will be summarised in tabular form by the intended dose group according to the cohort (Tideglusib 400mg and Tideglusib 1000mg) apart from disposition of subjects, protocol deviations, and background and demographic data which will be summarised by dose group and overall subjects. In the analysis to be conducted at completion of Cohort 1, the data will be summarised in tabular form for the Tideglusib 1000mg dose group only.

Listings will be sorted by dose group, subject number and time of assessment.

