2.2 Study Design

This is a single-blind, [REDACTED] study in adolescent and adult subjects with congenital or juvenile-onset type 1 myotonic dystrophy.

Approximately 16 subjects in total are planned to be enrolled and receive active treatment.

Participation for individual subjects will consist of an initial Screening of up to [REDACTED] (minimum of [REDACTED]) followed by a [REDACTED] treatment phase. After this, subjects in Cohort 1 will be treated with single-blinded 1000mg tideglusib once daily orally for 12 weeks and Cohort 2 will be treated with single-blinded 400mg tideglusib once daily orally for 12 weeks. A follow up visit will take place approximately [REDACTED] after the end of treatment visit.

Once [REDACTED] out of the [REDACTED] subjects from Cohort 1, who have received active treatment with [REDACTED] of tideglusib, have completed active treatment or discontinued from the study [REDACTED] the Data Safety Monitoring Committee (DSMC) will meet to review the available data and a recommendation will be made to the Sponsor whether Cohort 2 should be initiated. [REDACTED]

Active dosing of Cohort 2 will only start when the [REDACTED] tideglusib. No screening will take place for Cohort 2 until after the recommendation has been made from the DSMC, to the Sponsor, on if Cohort 2 should be initiated.

If the decision is made to enrol all Cohort 2 subjects on the [REDACTED] dose then the summaries and analyses described in this SAP will be updated to analyse all subjects from cohorts 1 and 2 as a single dose group in the final analysis at the end of the study.

All outputs specified in this SAP will be produced for the final analysis of the combined Cohort 1 and Cohort 2 subject data. The exceptions to this are the by subject line plots detailed within Sections 5.1.1, 5.1.2, 5.1.3 and 5.1.4.1, as well as the ad hoc Cohort 1 outputs specified in section 3.1. These specific outputs will only be produced for the Cohort 1 analysis (see Sections 3 and 3.1) and will be included in the final study report as a separate set of Cohort 1 specific analyses on this data cut. They will not be reproduced on subsequent data unless, at the end of the study, it is considered beneficial to produce these again as part of ad hoc analyses.

See protocol section 8.3 for full detail of the study design.

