7 SAFETY EVALUATION

7.1 Adverse Events

Adverse events will be coded using the latest MedDRA dictionary version.

A NTEAE is defined as an AE that started on or after the administration of placebo treatment but before the start of the administration of active treatment.

A TEAE is defined as an AE that started on or after the start of the administration of active treatment. If adverse event dates are incomplete and it is not clear whether the adverse event was treatment-emergent, it will be assumed to be treatment-emergent.

A "treatment period" TEAE is defined as an AE that started on or after the start of active treatment but before 2 days after active treatment was discontinued. A "post treatment period" TEAE is defined as an adverse event that started from 2 days after the active treatment was discontinued.

Adverse events of special interest (AESIs) are recorded if it is identified from a review of the haematology and biochemistry results that the subject has clinically significant liver function test elevation.

The following summaries of the total number of “treatment period” TEAEs, “post treatment period” TEAEs and all TEAEs (both “treatment period” and “post treatment period” TEAEs) will be provided at the event and subject levels as indicated:

- TEAEs (events and subjects).
- TEAEs by relationship to active treatment (events and subjects).
- TEAEs by severity (mild/moderate/severe) (events and subjects).
- Serious TEAEs (events and subjects).
- Serious active treatment related TEAEs (events and subjects).
- TEAEs leading to withdrawal (subjects only).
- TEAEs leading to discontinuation of active treatment (subjects only).
- Active treatment related TEAEs leading to discontinuation of active treatment (subjects only).
- TEAEs leading to death (subjects only).

The following summaries of NTEAEs will be provided at the event and subject levels as indicated:

- NTEAEs (events and subjects).
- NTEAEs by severity (mild/moderate/severe) (events and subjects).
- Serious NTEAEs (events and subjects).
- NTEAEs leading to withdrawal (subjects only).
- NTEAEs leading to death (subjects only).

In the above summaries, if a subject experienced more than one NTEAE/TEAE, the subject will be counted once using the most related event for the “by relationship to active treatment” summary and at the worst severity for the “by severity” summary.

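### NTEAE tables rest on a safety set that requires tideglusib, so they miss subjects lost in the placebo run-in; SAEs before first placebo enter no AE table (minor)

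*SAP*

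**What the plan says.** **Analysis set.** SAP Section 1 equates active treatment with tideglusib. Under SAP 4.1.1 the SAF "will include all subjects who had at least one administration of active treatment". It serves all summaries of several kinds of data, a list that ends with "administration of investigational product and safety evaluation data". Protocol 11.2 and 11.4 also put all safety summaries on the SAF and make no exception for the run-in. For percentages, the exceptions to the non-missing rule in SAP Section 1 include "adverse events where the percentage will be based on the number of subjects in the analysis set".

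**Event classes.** SAP 7.1 states: "A NTEAE is defined as an AE that started on or after the administration of placebo treatment". That window closes at the first tideglusib dose, where the TEAE window opens. An event whose incomplete date leaves its class unclear is taken as a TEAE. The planned NTEAE outputs are counts, severity, serious events, events leading to withdrawal, events leading to death, and tables by SOC and PT.

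**Collection.** Protocol 10.1.5 collects SAEs from consent and non-serious AEs from the first single-blind dose. Protocol 10.4.9 has serious occurrences before dosing recorded as SAEs rather than as medical history. The primary endpoint (protocol 8.1) evaluates AEs from baseline and SAEs from screening.

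**Run-in losses.** Protocol 7.1 replaces subjects who withdraw in the run-in, and protocol Section 11 names a class of run-in failures.

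**What else is reported.** SAP 4.1.1 says: "Listings of study data will be based on all subjects who were enrolled in the study". Its Enrolled Set is everyone who passed screening, and it is assigned only to disposition. On that set SAP 4.1 plans: "The number and percentage of subjects will be summarised by their reasons for withdrawal from treatment", and separately reasons for leaving the study.

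**The concern.** The SAP plans rows for run-in events that lead to withdrawal or death, then counts them in a set that a subject can join only by surviving the run-in and going on to tideglusib. The subjects most likely to fill those rows are excluded by definition.

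This has some weight because safety is the primary objective, there is no parallel placebo arm, and protocol 7.1 says that the run-in is there for the analysis. The NTEAE tables are therefore the only tabulated AE experience on placebo.

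The second gap is in classification. The SAE window of the primary endpoint opens at screening, but the earliest tabulated class opens at first placebo. The AE tables leave the stretch between the two uncovered, even for subjects who are later dosed.

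**Working it through.** **Step 1: classify events under the SAP definitions.** Each case assumes a clear onset date.

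| Event and subject | Class | In SAF | In an AE table | In the AE listing |
|---|---|---|---|---|
| SAE before placebo, screen failure | none | no | no | no |
| SAE before placebo, later given tideglusib | none | yes | no | yes |
| AE in run-in, leaves or dies before tideglusib | NTEAE | no | no | yes |
| AE in run-in, later given tideglusib | NTEAE | yes | yes | yes |
| AE after first tideglusib dose | TEAE | yes | yes | yes |

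The third row is the analysis-set gap. The first two rows are the classification gap. The screen failure also drops out of the listings, because these cover only enrolled subjects.

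**Step 2: what one lost subject does to a proportion.** The plan gives 8 dosed subjects per group (8 + 8 = 16). It gives no run-in withdrawal rate, so the counts below are assumptions. Let k run-in leavers each have an NTEAE and be replaced, and let no dosed subject have one.

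- One cohort, k = 1: the SAF shows 0/8; the placebo-exposed set gives 1/(8 + 1) = 11.1%.
- Both cohorts, k = 1, 2, 3: the SAF shows 0/16 each time; the placebo-exposed set gives 1/17 = 5.9%, 2/18 = 11.1% and 3/19 = 15.8%.
- If 2 dosed subjects also have an NTEAE and k = 1: 2/16 = 12.5% against 3/17 = 17.6%.

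For the withdrawal row, 0/8 against 1/9 also assumes that the leaver withdrew because of the event and that no dosed subject has a run-in event that later leads to withdrawal.

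**Step 3: how likely such a loss is.** Let p be the assumed probability that a subject leaves the run-in because of an AE. With replacement until 16 are dosed, independent subjects and no other run-in losses:

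P(at least one) = 1 − (1 − p)^16

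- p = 0: 0%
- p = 0.01: 1 − 0.8515 = 14.9%
- p = 0.02: 1 − 0.7238 = 27.6%
- p = 0.05: 1 − 0.4401 = 56.0%

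The run-in seems to last about two weeks: the Peabody test is done at run-in (protocol 10.2.12), and SAP Appendix 2 has a plot of it labelled Week -2. That is an inference from one label in a redacted schedule. It favours the low end of the range.

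**Step 4: SAEs before placebo.** With a clear date, the AE tables count none of them, whatever the true number.

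**The case against.** There is a fair case that little is lost. SAP and protocol agree on a SAF defined by tideglusib, so the two documents do not conflict. Using one set for NTEAEs and TEAEs keeps the placebo-to-active reading within the same subjects. An enrolled run-in leaver's events are in the full AE listing, the reason for withdrawal is in the disposition summary, and all AE and SAE data go to the DSMC (protocol 10.4.8). With about 16 dosed subjects, a listing can be read subject by subject. Non-serious run-in AEs lie outside the primary endpoint, and protocol 8.1 says that SAEs are evaluated from screening without prescribing a table. The shells are a separate document, not available here, and could name another population. The probabilities above are the chance of an assumed event, not the size of an error.

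All of this stands, and it is why the point is minor. It does not remove the gap: a listing gives no denominator, and a zero in the death row could be read as no run-in death when the row cannot count one.

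A reader might infer more than the documents support:

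- *That protocol 11.4 promises a table of every AE, so that omitting events before placebo contradicts it.* It does not. That section promises summaries by treatment and on the SAF, and an event before placebo belongs to no treatment.
- *That the withdrawal and death rows must be empty.* They need not be. A run-in event that leads to withdrawal or death after the first tideglusib dose is counted.
- *That the main safety result is biased.* The TEAE tables are unaffected.

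**Conclusion.** Both gaps are real on the text, and the point is minor. The planned NTEAE tables leave out anyone who withdraws or dies before tideglusib. A clearly dated SAE between consent and first placebo is in no AE table; it is listed if the subject was enrolled and is outside the listings if the subject failed screening. An SAE with an incomplete date of unclear class could instead be counted as a TEAE.

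The effect is confined to descriptive run-in tables and to the early part of the SAE window. Only serious events bear on the primary endpoint here. In one cohort, one lost subject is the difference between 0/8 and 1/9 (11.1%). The chance of at least one such loss runs from 0% to 56.0% as p goes from 0 to 0.05, and every value of p is assumed. If no such event occurs, the effect is nil. The conclusion assumes that the unseen shells make no exception.

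**What to change.** - Define a run-in set of all subjects who took at least one dose of run-in placebo. Use it for every NTEAE table and row, by intended cohort and overall, with N in each header.
- Add one SAE summary row for onset from consent to before first placebo, in all consented subjects.
- State that the SAE listing covers all consented subjects, so that screen failures are included.
- Keep the SAF for TEAEs.

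Assigning a cohort is no obstacle. Cohorts are filled in sequence (protocol 9.3), and SAP Section 1 already says that "data will be summarised in tabular form by the intended dose group according to the cohort", so a subject who never takes tideglusib still has one. No separate repeat of the Cohort 1 outputs is needed. SAP 2.2 says: "All outputs specified in this SAP will be produced for the final analysis of the combined Cohort 1 and Cohort 2 subject data", and its exceptions (line plots and ad hoc outputs) do not include the NTEAE tables.

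The cost is one analysis set, one table row and a sentence on the listing, from data already collected. The downside is that NTEAE and TEAE tables no longer share a denominator, so a before-and-after reading is no longer on the same subjects. Showing N in each header makes that visible.

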4.2 Protocol Deviations

Prior to database lock and prior to analysis of the Cohort 1 data, AMO Pharma Ltd will review the individual deviations and classify them as major or minor.

The number and percentage of subjects with at least one major protocol deviation will be summarised. Major protocol deviations will be summarised for each major deviation category. Major protocol deviation categories include:

- Subjects failing any eligibility criteria.
- Taking inadmissible concomitant medication.
- Subjects meeting withdrawal criteria but not withdrawn.
- Significant non-compliance with active treatment administration, [REDACTED] compliance.

Other major protocol deviations may be identified during the review.

Active treatment administration percentage compliance is given by:

$$\left(\frac{\text{Total amount of active treatment taken}}{\text{Total amount of active treatment expected to be taken}} \right) \times 100$$

The total amount (mg) of active treatment taken is given by:

$$\begin{aligned} & [REDACTED] (\text{sum of } [REDACTED] \text{ sachets dispensed} - \text{sum of } [REDACTED] \text{ sachets returned}) + \\ & [REDACTED] (\text{sum of } [REDACTED] \text{ sachets dispensed} - \text{sum of } [REDACTED] \text{ sachets returned}) \end{aligned}$$

Where active treatment dispensing commences from [REDACTED]

The total amount (mg) of active treatment expected to be taken for Cohort 1 subjects is:

1. Treatment period x [REDACTED], for subjects with no [REDACTED], where the treatment period is given by:

([REDACTED] or withdrawal date if prior to [REDACTED] - [REDACTED] date).

2. [REDACTED] x (treatment period prior to [REDACTED]) + [REDACTED] x (treatment period after [REDACTED]), where the treatment period prior to [REDACTED] is given by:

Date subject stopped taking [REDACTED] of active treatment - [REDACTED] date.

and the treatment period after [REDACTED] is given by:

[REDACTED] or withdrawal date if prior to [REDACTED] – date (taken from diary card) subject started taking [REDACTED] of active treatment + 1.

The total amount (mg) of active treatment expected to be taken for Cohort 2 subjects is:

Treatment period [REDACTED], where the treatment period is given in (1) above. [REDACTED] [REDACTED], the derivation of the total amount of active treatment expected to be taken for Cohort 2 subjects will be as per the calculation for Cohort 1 subjects.

Details of all protocol deviations (date, deviation category, specific details and classification of major or minor) and subject eligibility will be listed.

